14.9 Medical Outcomes Sleep Scale (MOS-Sleep)

Abrupt cessation of either alcohol or nicotine in dependent individuals can be associated with sleep disturbance, and overall improvement in clinical condition might be associated with improved sleep. Therefore, sleep behavior will be measured explicitly.

The MOS-Sleep is a self-report questionnaire consisting of 12 items to provide information across sleep dimensions.[61] The scale assesses the following sleep constructs: initiation (2 items), maintenance (2 items), respiratory problems (2 items), quantity (1 item), perceived adequacy (2 items), and somnolence (3 items). Subjects report the amount of time it took to fall asleep and the number of hours they slept each night over the past week. Subjects answer 10 additional questions on a 6-point Likert scale ranging from 1 = all of the time to 6 = none of the time.

14.10 Drinker Inventory of Consequences (DrInC)

The DrInC[3] contains 50 items assessed on a 3-point scale ranging from “never” (0 points) to “daily or almost daily” (3 points). These 50 items are further subdivided into 6 subscales: physical consequences (8 items; maximum score = 24); intrapersonal consequences (8 items; maximum score = 24); social responsibility consequences (7 items; maximum score = 21); interpersonal consequences (10 items; maximum score = 30); impulse control consequences (12 items; maximum score = 36), and control items (5 items; maximum score = 15), as well as a total consequences scale (45 items; maximum score = 135). The total consequences scale is the sum of all the subscales except for the control items subscale. A lower score indicates reduced adverse consequences of drinking as compared with a higher score. The control items subscale is the sum of 5 reverse-scored validity items.

14.11 Fagerström Test for Nicotine Dependence

The Fagerström Test for Nicotine Dependence[62] will be used to assess the behaviors associated with dependence on nicotine in potential study participants. The Fagerström Test for Nicotine Dependence will be administered at screening, and will, also, be repeated at the end of the double-blind phase and during the one month follow-up to ascertain behavioral consequences associated with nicotine dependence.

14.12 Demographics

Patient demographics will be collected for all subjects who sign a consent form. The subject's date of consent, date of birth, gender, race, marital status, education, employment status, income level and ethnicity will be recorded.

14.13 Drug Accountability

Drug accountability will be performed by recording the number of capsules dispensed and the number of capsules returned at clinic visits. The amount dispensed, daily dose prescribed, and amount returned will be reconciled and recorded at each visit. If the subject reports missing capsules that were not taken, this data will also be recorded and used to calculate total drug exposure. If the bottle was not returned, then the subject's self report of drug administration will be reported.

14.14 ECG

A 12-lead ECG will be obtained during screening and at visit 15. All 12-lead ECGs will be evaluated for HR, rhythm, and QTc intervals. Any abnormalities will be noted and an assessment of clinical significance will be done by a study physician or a qualified licensed medical provider.

14.15 Eligibility Checklist

The Eligibility Checklist which includes all inclusion and exclusion criteria will be reviewed in stages as follows: 1) after screening measures are completed and before scheduling the Study Day 1 visit and 2) prior to randomization on Study Day 1. If the subject was found not to be eligible at either of these timepoints, the reason(s) will be recorded. This data will be included in the study database for all subjects who signed the informed consent.

14.16 Medical History

A medical history will be taken on all potential study subjects to assure medical fitness and will be used to supplement the physician's general inquiry and physical examination.

14.17 Concomitant Medications

All medications (prescribed and over the counter medications plus herbal remedies) taken by the subject 90 days prior to the start of screening, during the screening period, and while taking investigational products will be recorded. Medications taken after the start of screening must be pre-approved by the study physician whenever possible to avoid interactions with the

investigational products. All medications reported by the subject or prescribed by the study physician will be recorded.

14.18 Timeline Follow-Back (TLFB)

The TLFB method of measuring alcohol and cigarette consumption will be used to construct a retrospective index of smoking and drinking behavior during the 3-month period before enrolling in the study. Thereafter, the consumption of alcohol or cigarettes between weekly visits will be recorded.[1] Days abstinent will refer to the number of days on which the subject consumes no alcohol or cigarettes. While subjects also will be provided with daily record cards as an aide-mémoire, only the TLFB data collected by a designated study staff member will be used in the efficacy analyses. From these data, we will determine both the PHDD and the point prevalence and continuous smoking abstinence rates. Self-reported reports of smoking cessation will be corroborated by measurement of breath CO level (see below).

Each site will receive training from the coordinating site, UVa, on how to administer the TLFB.

14.19 Carbon Monoxide (CO) Level

Expired carbon monoxide (CO) level will be measured using a Bedfont CO monitor. Self-reported abstinence will be verified by expired CO samples of <10 ppm. This will be measured at every in-clinic visit.

14.20 Quality of Life Enjoyment and Satisfaction Questionnaire (Q-LES-Q)

The Quality of Life Enjoyment and Satisfaction Questionnaire (Q-LES-Q)[64] is composed of 93 items, each containing responses on a 5-point scale that can range from 1 (“not at all or never”) to 5 (“frequently or all the time”). Ninety-one of these items are grouped into 8 summary scales. Five of the 8 summary scales are scored for all subjects and include: physical health/activities (13 items, maximum score = 65); subjective feelings (14 items, maximum score = 70); leisure time activities (6 items, maximum score = 30); social relationships (11 items, maximum score = 55), and general activities (14 items, maximum score = 70). The other 3 summary scales are scored when applicable, and these include: work (13 items, maximum score = 65); household duties (10 items, maximum score = 50), and school/course work (10 items, maximum score = 50). We measured satisfaction with medication and overall life satisfaction and contentment on individual item scales, each with a maximum score of 5.

14.21 Alcohol Craving Visual Analog Scales

The Alcohol Craving Visual Analog Scales will comprise 4 items on which subjects will be asked to rate themselves on how they feel “right now” by placing a mark along a 100-mm line anchored on the left by “not at all” and on the right by “extremely”. These items include: “*Right now I crave a drink*”; “*Right now I have a strong urge to have a drink*”; “*Right now I want to have a drink*”; and “*Right now I could refuse to have a drink*”. Scales of this type have been validated in a previous alcohol study by Johnson et al.[65] Whilst we are cognizant that other standardized measures of alcohol craving could have been collected (e.g., Obsessive Compulsive Drinking Scale,[66]) we chose the scale above because it also was validated and would correspond and be directly comparable to the nicotine craving measure described below.

14.22 Nicotine Craving Visual Analog Scales

The Nicotine Craving Visual Analog Scales will comprise 4 items on which subjects will be asked to rate themselves on how they feel “*right now*” by placing a mark along a 100-mm line anchored on the left by “*not at all*” and on the right by “*extremely*.” These items include: “*Right now, I crave a cigarette*”; “*Right now, I have a strong urge to have a cigarette*”; “*Right now, I want to have a cigarette*”; and “*Right now, I could refuse to have a cigarette*”. These scales are a derivative of those used in alcohol research by Johnson et al.[65]

14.23 The Tobacco Use History Questionnaire

This will be administered at screen. This self-report instrument provides data primarily on past cessation attempts, years smoking, other tobacco use, and past methods of cessation, and will be used to describe the past smoking behavior of the participants and to determine desire to quit.

14.24 Alcohol Use Disorders Identification Test (AUDIT)[67]

The Alcohol Use Disorders Identification Test (AUDIT)[67] is a well-validated measure of ascertaining the extent of alcohol-related problems.

14.25 Mini International Neuropsychiatric Interview (MINI)

The Mini International Neuropsychiatric Interview is a short 15 minute structured clinical interview. It is used for multi-site clinical trials and epidemiological studies to determine diagnoses of psychiatric disorders according to DSM-4 or ICD-10. The MINI we use will diagnose psychiatric disorders other than alcohol use disorder based on DSM-4 criteria. However, a DSM-5 diagnosis of mild to severe alcohol use disorder is required to be eligible for the study. In order to ascertain that a subject meets this criterion, if the subject answers “yes” to question I1 on the MINI, providers will proceed to ask the subject questions in both section I2 and I3. In addition, a supplemental sheet with an additional DSM-5 craving question will be added to the MINI. This sheet will also contain directions for scoring: all items coded YES will receive a score of one, including questions in I2, I3, and the supplemental craving question, and excluding question I 3 c. (regarding legal consequences). The total score will then be used to determine the severity grade of the subject’s alcohol use disorder. Severity grades include “no diagnosis” (a score of 0 to 1), “mild alcohol use disorder” (2 to 3), “moderate alcohol use disorder” (4 to 5), and “severe alcohol use disorder” (6 or greater).

The use of DSM-5 criteria rather than DSM-4 reflects a desire on the part of the research team to embrace the future of the Diagnostic and Statistical Manual and to be at the forefront of use of these carefully researched, revised guidelines. By including in one spectrum criteria formerly divided into two distinct, but clearly related, groups and by judging the results using a severity grade, we feel we will have a more accurate picture of a subject’s disorder and his or her suitability for participation. With this change, subjects who met one or two criteria in the former dependence section and also met one or more criteria in the abuse portion—and formerly would have failed to meet study inclusion criteria—will now be judged in a more overarching manner with an eye to the various ways the disorder may express itself. As we have included minimum use levels as part of our inclusion criteria, we feel that the modifications in the DSM-5 will prevent us from excluding those who are good candidates for the treatment proposed.

14.26 Salivary Cotinine Level

Cotinine is the primary metabolite of nicotine and has a half-life of about 19 hours.[68] Salivary cotinine level will be used as an additional objective measure of tobacco exposure for those who are still smoking. We propose the use of 15 ng/ml of saliva cotinine as a cut-off level to segregate non-smokers (≤ 15 ng/ml) from smokers (> 15 ng/ml). The SRNT Subcommittee on Biochemical Verification[69] and Seccareccia et al.[70] both recommend that a cut-off level of cotinine (15 ng/ml) be utilized for saliva, serum, or plasma samples.

Each site will collect saliva samples on all subjects before randomization and at visit 15. In the event that a subject is unable to attend visit 15, they may be asked to provide a cotinine sample, via mail, which will be used to verify abstinence. In such a case, a saliva collection kit and instructions will be mailed to the subject with a prepaid return address envelope.

Samples will be sent to a specialty lab where cotinine analysis will be performed on those who report abstinence. All sites will use the same saliva cotinine collection kits to maintain uniformity across the study.

14.27 Physical Examination

A physical examination of the oral cavity, head, eyes, ears, nose, and throat, cardiovascular system, lungs, abdomen, extremities, skin, neurological system, neck, lymph nodes, musculoskeletal system and general appearance will be performed.

14.28 Vital Signs

Vital signs to be assessed include sitting heart rate, respirations, temperature, and blood pressure. Weight will also be recorded at every visit in which vital signs are measured and height will be gathered at visits during which an ECG is performed.

14.29 Genotyping

It has been proposed recently that a single nucleotide polymorphism (SNP) variant of the glutamate receptor GluR5 gene (GRIK1) might predict adverse events to topiramate. Specifically, the SNP in intron 9 of the GRIK1 gene (rs2832407) appears to be particularly associated with adverse events.[71] Whilst it would not be reasonable to exclude participants from the study based upon the findings of a single unconfirmed report, because of the need to increase the generalizability of topiramate use, should this study demonstrate efficacy, we propose to type this SNP. Collecting DNA also will provide us with genetic samples that may be utilizable as science advances to understand further the neurobiology of excessive alcohol intake or smoking, and related behaviors.

Each site will collect blood samples for DNA extraction and genotyping. Samples will be collected for genotyping from subjects who consented to genetic testing. Samples will be shipped to University of Texas-MDACC where the DNA extraction and genotyping procedures will take place. **The blood collection for genotyping protocol can be found in Appendix VI.**

14.30 Baseline Drug Use and Other Drug Use

The Baseline Drug Use form will be used at screen to assess current and lifetime drug use. The Other Drug Use form will be used at visits 1-15 and at the one month follow-up visit to record any new drug use since the participant's last visit.

14.31 Contraceptive Method

The Contraceptive Method form will be used at screen and during visits 1-15. The form will record contraceptive method for females of childbearing potential or why the participant cannot bear children. For male participants, the form will be marked “Not Applicable” at the screening visit.

15 ANALYTICAL PLAN

15.1 Outcome Measures

The primary efficacy variables will be the PHDD for the drinking outcome and the continuous abstinence rate for the smoking outcome (during the last 4 weeks of treatment, i.e., weeks 15–18 inclusive), respectively. The secondary efficacy variables will be quality of life and measures of alcohol and nicotine craving. Exploratory outcomes include measures of dependence, and measures of nicotine and alcohol withdrawal including negative effect, as noted below:

1. Fagerström Test for Nicotine Dependence
2. Revised Clinical Institute Withdrawal Assessment for Alcohol scale (CIWA-Ar) [2]
3. Wisconsin Smoking Withdrawal Scale
4. Positive Affect Negative Affect Schedule (PANAS)
5. The Center for Epidemiologic Studies Depression Scale (CES-D)
6. Medical Outcomes Sleep Scale (MOS-Sleep)
7. The Drinker Inventory of Consequences (DrInC)[3]

Additional exploratory outcome variables will include other: 1) measures of drinking severity (i.e., DDD) and abstinence (i.e., percentage of days abstinent; PDA) averaged across either the entire double-blind period or the last 4 weeks of treatment, and 2) smoking measures including the point prevalence abstinence rate and the CO level over either the entire double-blind period or the last 4 weeks of treatment.

15.2 Standard Drink and Drinking Day Definitions

Drinking days are defined as the number of days in which the subject reported consumption of at least one standard drink. The data given by the subjects on amount and type of alcoholic beverage(s) consumed will be converted to SDUs (standard drink units). The following SDU formulas and conversions will be used:

$$(\# \text{ of Drinks}) \times (\text{oz drink}) \times (\% \text{ alcohol}) \times 2 = \text{Daily SDU}$$

$$\frac{\text{30 Day SDU Total}}{30} \times 7 = \text{Weekly SDU}$$

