Primary Efficacy Outcomes: The timeline follow-back (TLFB) method of measuring alcohol and cigarette consumption will be used to construct a retrospective index of smoking behavior during the 3-month period before enrolling in the study. Thereafter, the consumption of alcohol or cigarettes between weekly visits will be recorded.[1] Days abstinent will refer to the number of days on which the subject consumes no alcohol or cigarettes. While subjects also will be provided with daily record cards as an aide-mémoire, only the TLFB data will be used in the efficacy analyses. From these data, we will determine both the PHDD and the point prevalence smoking abstinence rates. Self-reported reports of smoking cessation will be corroborated by measurement of breath CO level, and, when necessary, urinary cotinine level (see below). PHDD is calculated as days for which the number of drinks was five or greater for men and four or greater for women, divided by the number of study days. [73]

Expired carbon monoxide (CO) level will be measured using a Bedfont CO monitor, and, when necessary, Accutest NicAlert strips Self-reported abstinence will be verified by expired CO samples of <10 ppm. Individuals who report smoking at screen and visit 1, but register less than 10ppm on the CO monitor will be re-tested with a NicAlert cotinine strip. Urinary cotinine scores of 3 or higher indicate tobacco usage.

Secondary Efficacy Outcomes:

1. The Quality of Life Enjoyment and Satisfaction Questionnaire (Q-LES-Q)
2. The Alcohol Craving Visual Analog Scales
3. The Nicotine Craving Visual Analog Scales

Exploratory Outcomes:

Psychological Assessments:

1. Fagerström Test for Nicotine Dependence
2. Revised Clinical Institute Withdrawal Assessment for Alcohol scale (CIWA-Ar),[2]
3. Wisconsin Smoking Withdrawal Scale
4. Positive Affect Negative Affect Schedule (PANAS)
5. The Center for Epidemiologic Studies Depression Scale (CES-D)
6. Medical Outcomes Sleep Scale (MOS-Sleep)
7. The Drinker Inventory of Consequences (DrInC)[3]

Study Retention and Compliance:

1. Attendance at regularly scheduled clinic visits
2. We shall assess compliance by comparing unused capsule count to dispensing logs and dosing records (number of capsules dispensed, number of capsules expected to be taken, versus the number returned).
3. Brief behavioral compliance enhancement treatment (BBCET)

Safety Assessments:

1. Medical history
2. Physical examination
3. Vital signs

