13.3 Subject Randomization

Prior to randomization, data essential for eligibility will be reassessed. Drinking and smoking requirements during the time period between the screening visit and visit 1 will be reassessed. All essential data for assignment to a treatment group will be collected by the study staff on the randomization form.

Assignment to a stratum during randomization will be based on the following: age of onset (≤ 25 or >25), drinks per drinking day (DDD) during the 90 days prior to screening (<8 or ≥ 8), average number of cigarettes smoked per day during the 90 days prior to screening, and gender. Calculations will be made using the formulas below.

$$\frac{\text{90 Day SDU Total}}{\text{\# Drinking Days}} = \text{Drinks per Drinking Day (DDD)}$$

$$\frac{\text{90 Day Cigarette Total}}{\text{90 Days}} = \text{Average \# Cigarettes per Day}$$

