Primary Outcomes Analytical Models:

We will use generalized linear models (GLM) to estimate treatment effects on PHDD and logistic regression for abstinence. We will adjust for baseline covariates on the same drinking or smoking variables. For the drinking and smoking variables, that baseline is the averaged value for the 90-day period prior to the screening visit. Other potential covariates shall include age, gender, and ethnicity. We also will consider the treatment period up to the TQD as an additional set of covariates for analyses that focus on the last 4 weeks of treatment. The residuals from our analyses will be checked for normality by computing their skewness and kurtosis and will be checked for homogeneity of variance by plotting them in a histogram and against predicted outcomes. Standard transformations will be employed to improve the distributions when required (i.e., square root or log transformation).

If, however, there is a differential attrition rate (i.e., if dropout is informative), we shall consider other approaches to handle repeated-measures data that can be adopted to obtain valid results.[7, 8]

Exploratory Analytical Models:

We also will use the more advanced two-part random-effects model[9, 10] to analyze the daily drinking and smoking record. Such a model can simultaneously characterize the frequency (odds of daily drinking or smoking being zero) and quantity (number of drinks on a drinking day or number of cigarettes smoked on a smoking day) of drinking and smoking outcomes, respectively. It is more efficient and can tackle non-normality in the drinking or smoking level. We also are interested in trajectory analysis of different treatments over time to capture differences in these outcomes. Such analysis is more clinically intuitive and could be more powerful than the analysis based on endpoint.

The Kaplan-Meier survival method will be used to compare time to achieve continuous abstinence between the treatment groups. Homogeneity between different arms will be tested with the log-rank test. Additionally, we will use the Cox proportional-hazards model to estimate the relative likelihood (i.e., magnitude of the treatment response) between the treatment groups for achieving continuous periods of abstinence. For the Cox regression model, potential confounding variables such as age of onset for alcoholism (less than 26 years old or 26 years and

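### DDD takes alcohol from days below one standard drink into its numerator but leaves those days out of its denominator, which overstates an exploratory outcome and can relabel strata near 8

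*Combined protocol and SAP*

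**What the plan says.** Section 15.2 sets the threshold for a drinking day: "Drinking days are defined as the number of days in which the subject reported consumption of at least one standard drink". It also converts reported beverages to SDU as number of drinks × ounces × alcohol fraction × 2. That formula can return values below 1, and no rounding rule is given.

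Section 13.3 stratifies on "drinks per drinking day (DDD) during the 90 days prior to screening", cut at 8, and computes DDD as the 90-day SDU total over the number of drinking days. Nothing limits the total to alcohol taken on those days. This is the only DDD formula in the document.

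Section 14.18 defines the opposite kind of day: "Days abstinent will refer to the number of days on which the subject consumes no alcohol or cigarettes". For alcohol, that means a day with none.

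DDD is also an exploratory outcome, over the double-blind period or the last 4 weeks of treatment (6.2, 15.1, 15.4). The exploratory two-part model in 15.4 has a "frequency (odds of daily drinking or smoking being zero") part and a quantity part for drinking days.

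**The concern.** The ratio does not use the same days above and below the line. A day with some alcohol but less than one SDU is neither a drinking day nor an abstinent day, yet its alcohol is spread over the other days as if it had been drunk then. The error can only be upward.

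At baseline this could put a participant just below 8 into the higher DDD stratum. On treatment it matters more. Section 9 directs counselling towards reduction goals for those who cannot stop after the quit date, so light days are a plausible result of improvement. A severity measure that can rise as a participant drinks less is hard to interpret.

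**Working it through.** **Plan's own figures.** The plan states no DDD figure to reproduce. Its sample size does reproduce: 10% vs 28%, power 0.80, two-sided alpha 0.017 (sidedness assumed), uncorrected test, gives 98 per arm. DDD does not enter that calculation.

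**Step 1: light days can occur.** With the 15.2 formula (serving sizes and strengths are my examples):
- 12 oz at 4%: 1 × 12 × 0.04 × 2 = 0.96 SDU
- 4 oz at 12%: 1 × 4 × 0.12 × 2 = 0.96 SDU
- 1 oz at 40%: 1 × 1 × 0.40 × 2 = 0.80 SDU
- For contrast, 12 oz at 5%: 1 × 12 × 0.05 × 2 = 1.2 SDU, which is a drinking day.

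**Step 2: the formula.** Let D be the days with at least 1 SDU, m the mean SDU on them, L the days above 0 and below 1 SDU, and a the mean SDU on those light days.
- As written: (mD + La)/D = m + La/D
- Consistent A (drop light-day alcohol from the numerator): m
- Consistent B (count every day with alcohol): (mD + La)/(D + L)

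The mismatch itself is the gap between the written value and A, namely La/D. The further gap from A to B is a change of threshold.

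**Step 3: baseline, 90 days.** The documents give no distribution of daily intake, so D, L, a and m are assumptions.

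| D | L | a | La/D |
|---|---|---|---|
| 80 | 5 | 0.8 | 4/80 = 0.05 |
| 60 | 10 | 0.8 | 8/60 = 0.13 |
| 60 | 30 | 0.9 | 27/60 = 0.45 |
| 30 | 30 | 0.8 | 24/30 = 0.80 |
| 20 | 40 | 0.96 | 38.4/20 = 1.92 |

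An example close to the cut: D = 60, m = 7.9, L = 10, a = 0.8. The total is 474 + 8 = 482. As written, 482/60 = 8.03 (stratum 8 or more); A gives 7.90; B gives 482/70 = 6.89. Both consistent versions fall below 8.

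The last row with m = 7: the total is 140 + 38.4 = 178.4. As written, 178.4/20 = 8.9; A gives 140/20 = 7.0; B gives 178.4/60 = 3.0.

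**Step 4: on treatment, 28 days**, assuming the 13.3 formula also applies to the outcome.

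| Pattern | Total SDU | As written | A | B |
|---|---|---|---|---|
| 1 day at 1 SDU, 10 at 0.8 | 9.0 | 9.0/1 = 9.0 | 1.0 | 9.0/11 = 0.82 |
| 2 days at 2 SDU, 10 at 0.8 | 12.0 | 12.0/2 = 6.0 | 2.0 | 12.0/12 = 1.0 |
| 4 days at 3 SDU, 8 at 0.8 | 18.4 | 18.4/4 = 4.6 | 3.0 | 18.4/12 = 1.53 |

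The first participant drinks about half as much as the third (9.0 vs 18.4 SDU) and has about twice the DDD (9.0 vs 4.6).

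**Step 5: no drinking days.** Six light days at 0.8 SDU and nothing else give 4.8/0 as written and 4.8/6 = 0.8 under B. Complete abstinence gives 0/0 under every version. No rule covers either case.

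**The case against.** The strongest reply is that light days may be rare and the baseline effect small. A participant needs days with a single weak or small serving: two such beers make 1.92 SDU and count. Under modest patterns the shift is 0.05 to 0.13, so relative to A only a drinking-day mean between about 7.87 and 8 is relabelled. The extreme pattern averages 178.4/90 × 7 = 13.9 SDU per week. If it continued into the 30 days before randomisation, it would meet the entry minimum for women (8) but not for men (15). All of this stands, and it limits the size of the point.

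Several stronger readings are tempting, but the documents do not support them:
- **That the mismatch moves DDD from 3.0 to 8.9.** It moves it from 7.0 to 8.9. The rest comes from replacing the one-drink threshold, which is a definitional choice.
- **That stratum shifts bias the trial.** The stratum is set before allocation by one rule for all arms, so a shift relabels a participant and no more.
- **That light days leave DDD undefined at randomisation.** If every day is below 1 SDU, the weekly total is below 7, under both entry minimums. The stratum's 90-day window before screening differs from the 30-day entry window, so it could happen only to someone with no day of 1 SDU or more for 90 days who then rose to entry level. On treatment, complete abstinence is the main route.
- **That a light day falls outside both parts of the two-part model.** The frequency part splits at zero, so a 0.96-SDU day is classified as non-zero. Only the quantity part's reference to drinking days needs aligning.
- **That the primary outcome is miscounted.** The percentage of heavy drinking days (PHDD) is worded in drinks ("PHDD is calculated as days for which the number of drinks was five or greater for men"), but 15.2 converts reported beverages to SDU and 13.3 labels an SDU ratio as drinks. SDU is the natural reading.

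**Conclusion.** The mismatch is real and always upward. It equals the light-day SDU total divided by the number of drinking days: about 0.05 to 0.13 at baseline under modest assumed patterns and 1.9 in an extreme one. On treatment it can dominate the value for someone who has cut down to light days, as with 9.0 against 0.8 to 1.0. That rests on three assumptions: the 13.3 formula serves the outcome, SDU are not rounded, and the illustrative patterns occur. How often they occur cannot be worked out from the documents.

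What is affected is the exploratory DDD outcome and stratum labels near 8. PHDD divides by study days, smoking abstinence does not use drinking data, and the 98 per arm does not depend on DDD. This is a minor correction, worth making because a rule followed as written gives a misleading value.

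**What to change.** - In 15.2, define a drinking day as any day with more than 0 SDU, and use it for DDD both as stratification factor and as outcome. Numerator and denominator then cover the same days, and for alcohol the definition complements the abstinent day in 14.18.
- Use the same definition in the quantity part of the two-part model, so that it matches the zero/non-zero split of the frequency part.
- State that the 13.3 formula, with the relevant period, applies to the DDD outcome.
- State how exploratory DDD is handled for participants with no drinking days. The new definition resolves the light-days-only case but not complete abstinence.
- Optionally, write the PHDD thresholds in SDU.

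If the one-drink threshold is to be kept, restricting the numerator to drinking days also removes the mismatch, but light days then remain neither drinking nor abstinent.

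The cost is a few sentences. The timeline follow-back data already hold what is needed, and the sample size does not change.
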